5.3. Lifestyle Considerations

Reproductive and contraceptive guidance is provided in Appendix 4 (Section 10.4).

5.3.1. Meals and Dietary Restrictions

Participants will be required to fast for at least 2 hours before being given a dose of LY3819253 (see SoA, Section 1.3). Per oral intake, should be limited to clear liquids for 4 hours prior to dosing. Standard meals will be administered while participants are resident at the study site.

5.3.2. Caffeine, Alcohol, and Tobacco

Participants must abide by the CRU restriction policy regarding consumption of alcohol and tobacco.

5.3.3. Activity

Participants should follow all site procedures and local guidelines for measures intended to prevent Covid-19 infection.

Participants should not engage in strenuous physical exercise or activities from 48 hours prior to dosing until discharge from the study or completion of all study procedures. When certain study procedures are in progress at the site, participants may be required to remain supine or sitting.

5.4. Screen Failures

Screen failures are defined as participants who consent to participate in the clinical study, but are not subsequently enrolled in the study.

Individuals who fulfill eligibility criteria, but are not randomized within the 14-day screening window, may still enroll in the study provided randomization occurs within 28 days of the first screening visit, and provided that they repeat site procedures to confirm Covid-19 status. These subjects do not need to be documented as screen failures. Subjects who are eligible, but are not enrolled within 28 days of their initial screening visit, will need to follow re-screen procedures described below.

For the purposes of assessing eligibility, screening clinical laboratory tests may be repeated if the result is considered likely due to a technical or handling error.

Individuals who do not meet the criteria for participation in this study (screen failure) due to a transient minor illness or concomitant medication may be re-screened if and when they later meet eligibility criteria.

Re-screened participants should be assigned a new screening number. When re-screening, all screening tests and procedures should be repeated (except safety laboratory analyses, if randomization is to occur within 28 days of the first screening tests). Individuals may be re-screened once, and must sign a new ICF.

6. Study Intervention

Study intervention is defined as any investigational intervention(s), marketed product(s), placebo, or medical device(s) intended to be administered to/used by a study participant according to the study protocol.

The SC injection site(s) will be peri-umbilical.

The study intervention will be given in the CRU by qualified CRU personnel as designated by the investigator. Study injections should be given by a limited number of personnel for consistency.

The site of administration of each injection will be recorded; when there is more than 1 injection, the same site will not be used, but another quadrant will be used.

6.1. Study Interventions Administered

Intervention	LY3819253	Placebo
Type	Biologic	Not applicable
Dose Formulation	solution	0.9% sodium chloride solution
Unit Dose Strength(s)	262.5 mg/2.1 mL vial (125 mg/mL)	Placebo
Planned Dosage Level(s)	Cohort 1: 350 mg Cohort 2: 700 mg Cohort 3: 700 mg	Not applicable
Route of Administration	SC injection	SC injection
Use	experimental	placebo
IMP and NIMP	IMP	IMP
Sourcing	From Lilly	Commercially available 0.9% sodium chloride solution
Packaging and Labeling	Study Intervention will be provided in glass vials and will be labeled appropriately	Commercially available 0.9% sodium chloride solution will be used as a placebo for this study

Abbreviations: IMP = investigational medicinal product; NIMP = non-investigational medicinal product;
SC = subcutaneous.

6.1.1. Injection volumes and formulation concentrations

Injection volumes are as follows:

Cohort (LY3819253 dose)	Number of injections and volumes
Cohort 1 (350 mg)	2x 1.4 mL
Cohort 2 (700 mg)	1x 1.4 mL + 2x 2.1 mL
Optional Cohort 3 (700 mg)	2x 1.9 mL + 1x 1.8 mL*

* Doses may be adjusted based on data review during the study, as described in Section 6.6. In this event, the number or volume of injections, or both, will be adjusted accordingly.

The LY3819253 formulation concentration will be 125 mg/mL in all cases.

6.1.2. In the Event of a Retrospective Positive Sterility Finding from Prepared Study Intervention

If a positive sterility finding occurs in the terminally sterile filtered study intervention, the participants who were dosed from the impacted batch should be contacted immediately and undergo a full physical examination including, but not limited to, blood pressure, pulse rate, and body temperature.

A blood sample should be collected for culture and assayed for inflammatory markers such as C-reactive protein and elevations in white blood cell counts.

If the signs and symptoms indicated a participant has a possible infection, they will be clinically managed, treated, and followed up until resolution. Any AEs will be recorded as appropriate.

6.2. Preparation/Handling/Storage/Accountability

The investigator or designee must confirm appropriate temperature conditions have been maintained during transit for all study intervention received, and any discrepancies are reported and resolved before use of the study intervention.

To protect blinding, the interventions must be prepared by unblinded site personnel qualified to prepare study intervention who are not involved in any other study-related procedures. Instructions for preparation will be provided by the sponsor.

Only participants enrolled in the study may receive study intervention, and only authorized site staff may supply or administer study intervention.

All study intervention must be stored in a secure, environmentally controlled, and monitored (manual or automated) area in accordance with the labeled storage conditions with access limited to the investigator and authorized site staff.

The investigator, institution, or the head of the medical institution (where applicable) is responsible for study intervention accountability, reconciliation, and record maintenance (i.e., receipt, reconciliation, and final disposition records).

Further guidance and information for the final disposition of unused study interventions are provided in the pharmacy manual.

6.3. Measures to Minimize Bias: Randomization and Blinding

Randomization tables for allocation of either LY3819253 or placebo will be prepared by the statistician or their designee.

This study will be participant- and investigator-blind.

Blinding will be maintained throughout the conduct of the study as described in the separate Blinding Plan.

Emergency codes will be available to the investigator. A code, which reveals the treatment group for a specific study subject, may be opened during the study only if the subject's well-being requires knowledge of the subject's treatment assignment.

In case of an emergency, the investigator has the sole responsibility for determining if unblinding of a subject's treatment assignment is warranted for medical management of the event. The subject's safety must always be the first consideration in making such a determination. If the investigator decides that unblinding is warranted, it is the responsibility of the investigator to promptly document the decision and rationale and notify Lilly as soon as possible.

If an investigator, site personnel performing assessments, or participant is unblinded during dosing, the participant must be withdrawn from further study intervention. If any amount of study intervention was administered, follow procedures according to the SoA, as described in Section 7.1.

Upon completion of the study, all codes must be returned to Lilly or its designee.

6.4. Study Intervention Compliance

Participants will receive study intervention directly from the investigator or designee, under medical supervision. The date and time of dosing in the clinic will be recorded in the source documents and in the CRF. The dose of study intervention and study participant identification will be confirmed at the time of dosing by a member of the study site personnel other than the person administering the study intervention.

6.5. Concomitant Therapy

All concomitant medications, whether prescription or over the counter, used at baseline and/or during the course of the trial, must be recorded on the Concomitant Medication eCRF.

Participants will be instructed to consult the investigator or other appropriate study personnel at the study site before taking any new medications or supplements during the study.

In general, concomitant medication should be avoided. Use of chronic, stable doses of hormone replacement therapy, thyroid replacement medications, or vitamin and mineral supplements is allowed.

Acetaminophen (1 g, maximum 3 g/24 hours) may be administered at the discretion of the investigator for treatment of headache, etc. However, acetaminophen may not be given within 24 hours before dosing.

If the need for concomitant medication (other than acetaminophen) arises, inclusion or continuation of the participant may be at the discretion of the investigator after consultation with a Lilly clinical pharmacologist or CRP.

Any medication used during the course of the study must be documented.

All vaccines are prohibited until study completion.

6.6. Dose Modification

Depending on the results of a given trial-level safety review, the dose of the subsequent cohort(s) may be adjusted. Because these adjustments to dose levels are allowable changes permitted by the protocol, they would not require a protocol amendment.

6.6.1. Dose-Escalation Criteria

Data will be evaluated on an ongoing basis.

After at least 4 participants assigned to LY3819253 have completed Day 4 in a given cohort, all safety data up to this cutoff date will be reviewed to determine whether the next cohort can be randomized after agreement between Lilly's medical monitor and the investigator. Safety and tolerability data will be the primary criteria guiding dose escalation.

The investigator and the Lilly sponsor team are responsible for determining any dose decisions. The investigator(s) will remain blinded and the Lilly sponsor team will be unblinded during these reviews. All available data from previous cohorts will be reviewed.

If temporary stopping criteria are met (Section 6.6.3), dosing will be temporarily halted and no further participants will be dosed until a full safety review of the study has taken place.

6.6.2. Access to Data during the Study

A limited number of unblinded Lilly study team personnel will have access to safety and/or PK data during the study.

6.6.3. Temporary Stopping Criteria

Dosing will be temporarily halted, and no further participants will be dosed until safety data available at that point have been reviewed:

- pending discussion between the investigator and sponsor, if 3 or more participants develop AEs that are considered to be related to study treatment;
- if 1 or more participants develop AEs that are considered to be related to study treatment and that are serious (SAEs) or graded as severe.

This table describes the location of AE-related information in this protocol.

Topic	Location
Definition of AEs	Section 10.3.1
Assessment of Intensity/Severity	Section 10.3.3

Changes to the planned dosing schedule must be appropriately documented and communicated with the study personnel and the IRB/IEC before dosing continues.

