8.2.5. Injection Site Reaction Assessment

Injection site assessments using the ISR CRF, VAS if required (see below), and an exploratory tool (Scarletred) will be performed at times specified in the SoA (Section 1.3).

Injection site pain assessments are part of the solicited and spontaneous ISR assessments. The baseline assessment, and all positive responses of pain from then on, will require an additional assessment using the Pain VAS.

As there are multiple injections for each dose, ISR assessments will be done for each injection. Manifestations of a local ISR may include erythema, induration, pain, pruritus, and edema. Injection site findings will be captured on the eCRF.

Injection site reactions, if recorded as a result of the prespecified (or solicited) assessment, will be recorded as AEs only if they qualify as SAEs.

If a spontaneous (or unsolicited) ISR is reported by a participant or investigator, the ISR CRF will be used to capture additional information about this reaction (for example, degree and area of erythema) at additional visits until resolution of the event.

The VAS is a well-validated tool (Williamson and Hoggart 2005) to assess injection site pain; it is presented as a 100-mm line anchored by verbal descriptors, usually "no pain" and "worst imaginable pain." The participant will be asked to rate any pain at the injection site on a scale of 0 to 100 on the line, as soon as possible following each injection.

In addition, the exploratory tool (Scarletred) will be used to acquire exploratory ISR data at each of the time points where the ISR data is being collected by administration of the ISR CRF. Failure to take this assessment at any of the indicated time points will not result in a protocol deviation.

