10.3.2. Definition of SAE

Please note: If an event is not an AE per definition above, then it cannot be an SAE.

An SAE is defined as any AE that:
a. Results in death
b. Is immediately life-threatening The term 'life-threatening' in the definition of 'serious' refers to an event in which the participant was at risk of death at the time of the event. It does not refer to an event, which hypothetically might have caused death, if it were more severe.
c. Requires inpatient hospitalization or prolongation of existing hospitalization 
 ● In general, hospitalization signifies that the participant has been admitted to hospital for >”23 hour observation” and/or treatment that would not have been appropriate in the physician’s office or outpatient setting. Complications that occur during hospitalization are AEs. If a complication prolongs hospitalization or fulfills any other serious criteria, the event is serious. When in doubt as to whether “hospitalization” occurred or was necessary, the AE should be considered serious. ● Hospitalization for elective treatment of a pre-existing condition that did not worsen from baseline is not considered an AE.
d. Results in persistent disability/incapacity 
 ● The term disability means a substantial disruption of a person’s ability to conduct normal life functions. ● This definition is not intended to include experiences of relatively minor medical significance such as uncomplicated headache, nausea, vomiting, diarrhea, influenza,

and accidental trauma (for example, sprained ankle) which may interfere with or prevent everyday life functions but do not constitute a substantial disruption.

e. Is a congenital anomaly/birth defect

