10.3.3. Recording and Follow-Up of AE and/or SAE

AE and SAE Recording

When an AE/SAE occurs, it is the responsibility of the investigator to review all documentation (for example, hospital progress notes, laboratory reports, and diagnostics reports) related to the event.
 
The investigator will then record all relevant AE/SAE information in the CRF.
 
It is not acceptable for the investigator to send photocopies of the participant’s medical records to Sponsor or designee in lieu of completion of the AE/SAE CRF page.
 
There may be instances when copies of medical records for certain cases are requested by Sponsor or designee. In this case, all participant identifiers, except the participant number, will be redacted on the copies of the medical records before submission to Sponsor or designee.
 
The investigator will attempt to establish a diagnosis of the event based on signs, symptoms, and/or other clinical information. Whenever possible, the diagnosis (not the individual signs/symptoms) will be documented as the AE/SAE.

Assessment of Intensity/Severity

The investigator will make an assessment of intensity for each AE and SAE reported during the study and assign it to one of the following categories.
 
Mild: Mild symptoms causing no or minimal interference with usual social and functional activities, with intervention not indicated.
 
Moderate: Moderate symptoms causing greater than minimal interference with usual social and functional activities, with intervention indicated.
 
Severe: Severe symptoms causing inability to perform usual social and functional activities, with intervention or hospitalization indicated.

An event is defined as ‘serious’ when it meets at least 1 of the predefined outcomes as described in the definition of an SAE, NOT when it is rated as severe.

Assessment of Causality

The investigator is obligated to assess the relationship between study intervention and each occurrence of each AE/SAE.

A “reasonable possibility” of a relationship conveys that there are facts, evidence, and/or arguments to suggest a causal relationship, rather than a relationship cannot be ruled out.

The investigator will use clinical judgment to determine the relationship.

Alternative causes, such as underlying disease(s), concomitant therapy, and other risk factors, as well as the temporal relationship of the event to study intervention administration will be considered and investigated.

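### As most naturally read, the automatic dosing halt misses a severe, treatment-related but non-serious injection site reaction found only at a scheduled check

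*Protocol*

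**What the plan says.** Protocol 6.6.3 halts dosing temporarily on either of two conditions, both expressed in AEs. The first, subject to discussion between investigator and sponsor, applies "if 3 or more participants develop AEs that are considered to be related to study treatment". The second applies "if 1 or more participants develop AEs that are considered to be related to study treatment and that are serious (SAEs) or graded as severe". A small table in the same section sends the reader to 10.3.1 for what an AE is and to 10.3.3 for severity.

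Section 8.2.5 deals with ISRs by how they come to light. For the scheduled route: "Injection site reactions, if recorded as a result of the prespecified (or solicited) assessment, will be recorded as AEs only if they qualify as SAEs". The paragraph on the other route opens "If a spontaneous (or unsolicited) ISR is reported by a participant or investigator" and asks for further follow-up on the ISR form; it sets no such limit on AE recording. Each dose is split, and "ISR assessments will be done for each injection".

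On grading, 10.3.3 states: "The investigator will make an assessment of intensity for each AE and SAE reported during the study". Its top category reads: "Severe symptoms causing inability to perform usual social and functional activities, with intervention or hospitalization indicated". The same section says that a severe rating does not by itself make an event serious. Among the seriousness criteria in 10.3.2 is: "Requires inpatient hospitalization or prolongation of existing hospitalization".

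Section 4.1.2 expects ISRs and how severe they are to dominate the sentinel assessment in Cohort 1. Cohorts 2 and 3 have no sentinels.

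**The concern.** For one class of event, the automatic pause turns on how a reaction was detected and not on how bad it was. That class belongs to the signal the protocol itself expects to matter most when SC dosing begins.

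At stake is whether participants not yet dosed receive the injections before anyone is obliged to stop and look. Section 4.2 describes this as the first human study of the new formulation by the SC route. Cohort 2 is the first to receive 2.1 mL injections: the largest single injection rises from 1.4 to 2.1 mL (2.1/1.4 = 1.5, or +50%), and the total rises from 2 × 1.4 = 2.8 mL to 1.4 + 2 × 2.1 = 5.6 mL.

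**Working it through.** The documents give no operating characteristic for the halt rule, so there is no figure to reproduce. The check is a reading of the sections together, followed by counts and an illustration of what the fix would cost.

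**1. Tracing one severe, treatment-related ISR through the sections**

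| How found | Serious? | An AE under 8.2.5? | Graded under 10.3.3? | Second 6.6.3 criterion |
|---|---|---|---|---|
| Scheduled check | Yes | Yes | Yes | Met |
| Spontaneous report | No | Not excluded | Yes, once recorded | Can be met |
| Scheduled check only | No | No | No | Not met |

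The third row also adds nothing to the first criterion, which counts AEs too.

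**2. How much is left in the third row.** Severe in 10.3.3 means that intervention or hospitalization is indicated. Inpatient hospitalization makes the event serious under 10.3.2, and the medical-judgement clause there could capture others. What remains is a reaction that stops usual activities and needs intervention but meets no seriousness criterion.

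**3. Opportunity for scheduled detection (SoA, injection site row).** Postdose checks are at 1, 10, 30 and 240 minutes (4 on Day 1), at 24 hours (5 so far) and on Days 3 to 7 (10 in all). Per injection, Day 1 gives 4 × 2 = 8 assessments for a Cohort 1 participant and 4 × 3 = 12 for a Cohort 2 participant. The SoA lists AE review on Day 1 as predose only, and then on each of Days 2 to 7. An early reaction may well be seen first at a scheduled check. These counts do not show how often it would be seen only there.

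**4. Who a halt could protect, with nine per cohort (7 LY3819253, 2 placebo)**
- Cohort 1: after the 1:1 sentinel pair, 9 − 2 = 7 remain (6 LY3819253, 1 placebo). The sentinel decision already gates them. Once they are dosed on the next day, only replacements are left, because Cohort 2 waits for the 6.6.1 review.
- Cohort 2: up to 9 − 1 = 8 if participants are dosed one at a time, and none if all are dosed together. The documents do not say which is planned.

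**5. How often the fix would pause dosing.** Assume a severe related ISR rate p per LY3819253 participant, independence, and zero on placebo. With k LY3819253 participants dosed before others, the chance of at least one is 1 − (1 − p)^k.

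| k | Situation | p = 1% | p = 2% | p = 5% |
|---|---|---|---|---|
| 1 | Cohort 1 sentinel | 1.0% | 2.0% | 5.0% |
| 3 | Cohort 2, three dosed before the rest | 3.0% | 5.9% | 14.3% |
| 6 | Cohort 2, one at a time, last on LY3819253 | 5.9% | 11.4% | 26.5% |
| 7 | Cohort 2, one at a time, last on placebo | 6.8% | 13.2% | 30.2% |

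These are upper limits on the added pauses, since a severe ISR reported spontaneously can already trigger the halt.

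**6. Why non-severe solicited ISRs should stay out of the three-participant criterion.** If half of 7 LY3819253 participants had some ISR, P(at least 3) = 1 − (1 + 7 + 21)/128 = 77.3%. At 70% it is 1 − (0.0002 + 0.0036 + 0.0250) = 97.1%. Counting them would make the criterion fire almost routinely. All rates in steps 5 and 6 are assumptions; the documents give none.

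**The case against.** The strongest reply is textual. Section 6.6.3 speaks of participants developing AEs, not of AEs entered on a form, and it points to 10.3.1, whose broad definition would cover a severe ISR. On that view 8.2.5 only governs recording and the halt already applies. This reading is available. It is the less natural one, because 8.2.5 is the specific rule for ISRs, and being graded severe depends on 10.3.3, which grades reported AEs and SAEs. If it is the intended reading, the added clause simply states it.

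The second reply is practical. A reaction this disabling, in a participant resident at the unit until Day 7, would probably be mentioned by the participant or raised by the investigator. Either makes it spontaneous under 8.2.5, and 8.3.1 collects AEs throughout participation. That stands, and it makes the solicited-only case uncommon, though not impossible.

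Third, other gates exist. The rest of Cohort 1 is dosed only after a positive sentinel decision, 6.6.1 provides ongoing evaluation and a review of all safety data before the next cohort, and section 8 requires immediate discussion of safety concerns. These stand as well. They rest on judgement, and the 6.6.1 cohort review does not automatically stop dosing within a cohort.

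Two stronger readings are tempting. A reader might infer that severe solicited ISRs would go unreviewed, or that a whole next cohort could be dosed without anyone considering them. The gates just listed rule that out. A reader might also treat the different wording of the review minimum in 4.1.2 and 6.6.1 as a further weakness. Both are minimums and can be met together, so the difference is editorial and lends this point no support.

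**Conclusion.** The point holds in a limited form. On the most natural reading of 6.6.3, 8.2.5 and 10.3.3, a severe, related, non-serious ISR found only at a solicited check does not trigger the automatic halt. Section 10.3.1 leaves room for the opposite reading, which is itself a reason to settle the matter before dosing.

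The practical reach is small: mainly replacements and any participants still to be dosed where a cohort is staggered. How often such a reaction would be solicited only cannot be estimated from the documents, and the check counts and volumes above do not measure it. The participant counts assume nine per cohort at 7:2. This is a cheap safety improvement; the documents do not show that participants are left without safety oversight.

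**What to change.** In 6.6.3, extend the second criterion with: *or any injection site reaction considered related to study treatment and graded severe, whether solicited or spontaneous*. The relatedness condition should stay, since both existing criteria carry it. Add one sentence stating that, for this purpose, solicited ISRs are graded with the mild, moderate and severe categories of 10.3.3. Leave non-severe solicited ISRs out of the three-participant criterion. Section 8.2.5 can keep its AE recording rule unchanged.

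The cost is one clause and one grading sentence. ISR severity is already part of the exploratory endpoint, so the extra work at the site is small. The downside is an occasional temporary pause. At the assumed 1% to 5% severe rate, the chance of stopping next-day dosing in Cohort 1 is 1% to 5%. In Cohort 2, the chance of stopping anyone still to be dosed runs from zero if all are dosed together to at most 7% to 30% if they are dosed one at a time.
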